with the variance components defined as previously. These data suggest true four-year and one-year correlations of 0.85 and 0.91, respectively. Interpolating to 6 and 18 months, the true correlations in TOHP are estimated to be 0.92 and 0.90, respectively. Given three visits with three measurements each, we would expect to observe correlations of approximately 0.84 (6 months) and 0.83 (18 months). These figures lead to estimated variances for the change in means of 38.03 (standard error = 6.17) for 6 months and 40.41 (standard error = 6.36) for 18 months of observation.

Allocation of Subjects

Clinic-specific allocations are presented in Table 1.

Power_Calculations

Power calculations assume a two-sided test with significance level 0.05 and use the following formula:

Power =
$$1 - \Phi \left[z_{1-\alpha/2} - \frac{d}{\frac{\sigma^2}{n_1} + \frac{\sigma^2}{n_0}}\right]$$

where: $\Phi[\]$ = the area to the right of [] on the standard normal curve

 $z_{1-\alpha/2} = 1.96$

d = the difference in BP change between the intervention and comparison groups

 σ^2 = 6.172 for supplements and 6.362 for lifestyles

 n_1 = the number in the active intervention group

 n_0 = the number in the control group

The estimated powers associated with the expected numbers in the proposed study design are given in Table 12. All tests will have at least .90 power to detect a 2 mm Hg change in DBP.

POWER CALCULATIONS: SBP

Estimate of Variance

The same methods used for DBP have been used to estimate the components of variance for SBP. The variance of the mean BP (\vec{x}) at either baseline or termination can again be written as:

$$V_{(\vec{x})} = \sigma^2 = \sigma^2_p + \sigma^2_A/N + \sigma^2_e/NK$$

where: σ^2_{p} = between-person variance

 σ^2 A = between-visit variance

 σ^2 = within-visit variance

N = number of visits = 3

K = number of measurements per visit = 3

The variance of the difference between the baseline and termination values is a function of σ (defined above) and the tracking correlation (the variation in BP over time):

$$V(\overline{x}_1 - \overline{x}_2) = 2\sigma^2(1-\rho)$$

where:

- mean SBP at baseline

- mean SBP at termination

- the observed tracking correlation of the BP means over an average of 18 months of follow-up for the lifestyle interventions and six months of follow-up for the supplement interventions

Estimating the components of the variance of the mean BP at either base-1. line or termination

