Again, using estimates from Rosner and Polk (104) and from the HDFP (102):

$$\sigma^2 = 233.13$$

$$\sigma^{2}_{p} = 233.13$$
 $\sigma^{2}_{A} = 43.39$
 $\sigma^{2}_{e} = 13.16$

$$\sigma_{\rm e}^2 = 13.16$$

Therefore, $V(\bar{x})$, the estimated variance of the mean SBP (averaged over three visits with three readings per visit) at baseline or termination is 249.06.

2. Estimating the tracking correlation

> Estimates for 4-year tracking correlations come from data from Wales (103); estimates for 1-year tracking correlations come from Rosner and Polk (104). In addition, the relation between observed and true tracking correlations is estimated by the following equation:

$$\rho_{\text{true}} = \rho_{\text{obs}} \times (\sigma_{\text{p}}^2 + \sigma_{\text{A}}^2/N + \sigma_{\text{e}}^2/NK)/\sigma_{\text{p}}^2$$

For SBP, the observed and true tracking correlations are .67 and .83 for 4-years and .81 and .85 for 1-year, respectively. Interpolating to 6 and 18 months, the true correlations in TOHP are estimated to be .853 and .847. Given three visits with three measures each, we would expect to observe correlations of approximately .80 (6 months) and .79 (18 months). These figures lead to estimated variances for the change in means of 99.62 (standard error = 9.98) for 6 months of observation and 104.61 (standard error = 10.23) for 18 months of observation.

Allocation of Subjects

The same clinic-specific allocations shown in Table 1 are used.

Power Calculations

The estimated powers associated with the expected numbers are given in Table 13. All tests will have between .87 and .98 power to detect a 3 mm Hg change in SBP.

DATA ANALYSES

The data analyses will be performed by the CC, with input from other trial investigators, for review by the Data and Safety Monitoring Committee at its semi-annual meetings.

This study will allow for the evaluation of seven different interventions. For each intervention, baseline characteristics will first be examined in the intervention and comparison groups to see if randomization achieved equal allocation. The primary factors of interest are those to be affected by the trial, including DBP, body weight, dietary components, and exercise frequency. Other variables that might influence change in DBP will also be examined.

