Session 9

Review of First Food Exchange Diaries Healthy Eating (U.S. Dietary Goals) Individual Planning Supervised Exercise

Session 10

Food Exchange Scoring System Self-reinforcement techniques Individual Planning Supervised Exercise

Sessions 11-14

Outlines to be developed. All of these sessions will include: Individual Planning Supervised Exercise

-FINAL TOHP STRESS MANAGEMENT PROGRAM COMPONENT SEQUENCING

MONTH	SESSION	TYPE	Weekly Sessions	
M01	01		Individual orientation & intervention data collection	-
M01			Group building + Slow-Paced Breathing	-
1	03	1 1	Bernstein & Borkovec Progressive Muscle Relaxation (B&B PMR) #1	1 1
	[04		B&B PMR #2: Emphasis on minimal tension & applications	1
	05		Relaxation using Imagination	1 (
M02			Applied Relaxing Imagination: Desensitization	1
M02			Applied Relaxing Imagination: Positive Covert Rehearsal	MI
M02	08	G	Clinically Standardized Meditation (CSM)	
			Biweekly Sessions	
М03	09	G	Time Management #1	
	10			M2
M04	11	G		
M04	12	G	Changing Stressful Thinking Patterns #1	
			Monthly Sessions	
MO5	13	G	Changing Stressful Thinking Patterns #2	1
M06	14	I	Individual session. Focus: Long term maintenance & applied skills	
	15			1 1
M08	16	G	Positive Cognitive Coping Strategies	1
	17			1.3
M10	18	G	Active Listening + Assertiveness Training #2	op [
			Anger Management #1	M4
M12	20	G	Anger Management #2	
			Bimonthly Sessions	
M14	21	G	General Problem Solving Session #1	45
	22		General Problem Solving Session #2	146
M18	23	G	General Problem Solving Session #3	M 7

Type: G or I: Type of session, group or individual

M1, etc.: Represents 10 min. segment on long term maintenance

Table 11

DOSAGES AND NUMBER OF DAILY PILLS REQUIRED FOR TOHP SUPPLEMENTS INTERVENTIONS

Supplement	Dosage/Day	Dosage/Pill	Pills/Day
Calcium carbonate	1000 mg	500 mg	2
Magnesium diglycine	360 mg	60 mg	6
Potassium	60 mmoles	20 mmoles	3
Fish oil*	3000 mg	500 mg	6

^{* 1000} mg capsule of Promega contains 500 mg of fish oil.

Table 12
SAMPLE SIZE AND POWER ESTIMATES: DBP

	Size of Comparison		Average	Δ for	
Intervention	Active	Control	Expected Follow-up	80% Power (mm Hg)	$\Delta = 2 \text{ mm Hg}$
Sodium Restriction	327	416	18 months	1.32	.99
Weight Reduction	308	232	18 months	1.55	. 95
Stress Management	242	319	18 months	1.66	. 92
Calcium	237	234	6 months	1.60	.94
Magnesium	227	234	6 months	1.61	. 94
Potassium	207*	203*	6 months	1.70	.91
Fish oil	199*	203*	6 months	1.72	. 90

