 $[\]star$ Estimated numbers based on rerandomizing 85% of Stage 1 participants plus 6 additional in each group at Baltimore

Table 13
SAMPLE SIZE AND POWER ESTIMATES: SBP

	Size of Comparison		Average	Δ for	
Intervention	Active	Control	Expected Follow-up	80% Power (mm Hg)	$\Delta = 3$ mm Hg
Sodium Restriction	327	416	18 months	2.12	. 98
Weight Reduction	308	232	18 months	2.49	. 92
Stress Management	242	319	18 months	2.68	.88
Calcium	237	234	6 months	2.50	.92
Magnesium	227	234	6 months	2.59	.91
Potassium	207*	203*	6 months	2.70	. 88
Fish oil	199*	203*	6 months	2.75	.87

 $[\]star$ Estimated numbers based on rerandomizing 85% of Stage 1 participants plus 6 additional in each group at Baltimore

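### Six of the 14 rows in Tables 12 and 13 do not follow from the protocol's own formula: both stress management rows understate power, and the four supplement SBP rows slightly overstate it

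*Protocol*

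**What the plan says.** The section on power for DBP fixes the method: "Power calculations assume a two-sided test with significance level 0.05 and use the following formula". The formula shown there divides the target difference by the standard error of a difference between two means. The same section gives the spread of the DBP change: "estimated variances for the change in means of 38.03 (standard error = 6.17) for 6 months and 40.41 (standard error = 6.36". The section on power for SBP gives the corresponding figures: "variances for the change in means of 99.62 (standard error = 9.98) for 6 months of observation and 104.61 (standard error = 10.23". In each, the quantity labelled a standard error is the square root of the variance of an individual's change, so it serves as the SD in the formula.

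The results are in Table 12 ("SAMPLE SIZE AND POWER ESTIMATES: DBP") and Table 13 ("SAMPLE SIZE AND POWER ESTIMATES: SBP"). Each row lists the active and control sizes, the difference detectable with 80% power, and the power at 2 mm Hg (DBP) or 3 mm Hg (SBP). The stress row of Table 12 reads "Stress Management 242 319 18 months 1.66 . 92". Table 13 uses the same sizes and gives 2.68 and .88.

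Two sentences summarise the tables. For DBP: "All tests will have at least .90 power to detect a 2 mm Hg change in DBP". For SBP: "All tests will have between .87 and .98 power to detect a 3 mm Hg change in SBP".

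**The concern.** The stress rows conflict with the weight reduction rows beside them, before any power is computed. Both interventions use the same SD, so the detectable difference depends only on 1/n1 + 1/n0. For stress this is 1/242 + 1/319 = .00727. For weight it is 1/308 + 1/232 = .00756. Stress should therefore detect a slightly smaller difference than weight. The tables print a larger one for both endpoints: 1.66 against 1.55, and 2.68 against 2.49. The printed sizes and the printed results cannot both be right.

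The supplement SBP rows raise a different doubt. One SD is stated for all four (9.98), yet their detectable differences imply 9.68, 9.92, 9.76 and 9.84. All four depart in the favourable direction.

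What is at stake is whether the protocol states correctly what each comparison can resolve. For stress management this includes the primary endpoint.

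**Working it through.** **Inputs.** Two-sided 0.05, z = 1.96. SD of DBP change: 6.36 (lifestyle), 6.17 (supplements). SD of SBP change: 10.23 (lifestyle), 9.98 (supplements). Group sizes as printed in Tables 12 and 13.

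**Formulas.** SE = SD × √(1/n1 + 1/n0). Detectable difference at 80% power = (1.960 + 0.842) × SE. Power = Φ(d/SE − 1.96), with d = 2 for DBP and d = 3 for SBP. The extracted text shows no square root in the denominator. I take that as loss in reading the PDF, because the root form reproduces the eight rows below.

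**Rows that reproduce** (difference in mm Hg / power):

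| Row | Stated | Computed |
|---|---|---|
| Sodium, DBP | 1.32 / .99 | 1.317 / .989 |
| Weight, DBP | 1.55 / .95 | 1.549 / .951 |
| Calcium, DBP | 1.60 / .94 | 1.593 / .940 |
| Magnesium, DBP | 1.61 / .94 | 1.610 / .936 |
| Potassium, DBP | 1.70 / .91 | 1.707 / .907 |
| Fish oil, DBP | 1.72 / .90 | 1.724 / .901 |
| Sodium, SBP | 2.12 / .98 | 2.118 / .978 |
| Weight, SBP | 2.49 / .92 | 2.491 / .921 |

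All eight powers agree to two decimals. The differences agree to within 0.01 mm Hg.

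**Stress management.** √(1/242 + 1/319) = .08525.
- DBP: SE = 6.36 × .08525 = .542. Difference = 2.802 × .542 = 1.519. Power = Φ(2/.542 − 1.96) = .958. Stated: 1.66 and .92.
- SBP: SE = 10.23 × .08525 = .872. Difference = 2.443. Power = Φ(3/.872 − 1.96) = .931. Stated: 2.68 and .88.
- Ratios: 1.66/1.519 = 1.093 and 2.68/2.443 = 1.097. Power shortfalls: 3.8 and 5.1 points.

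A noncentral t calculation gives .958 and .930. A one-sided test, or the supplement SD, moves power further from the stated values. With 320 controls the results are 1.518/.958 and 2.442/.931. None of these gives .92 and .88.

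**Supplement SBP rows** (SD 9.98):

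| Row | Sizes | SE | Stated | Computed | Power gap (points) |
|---|---|---|---|---|---|
| Calcium | 237 / 234 | .920 | 2.50 / .92 | 2.577 / .904 | 1.6 |
| Magnesium | 227 / 234 | .930 | 2.59 / .91 | 2.605 / .897 | 1.3 |
| Potassium | 207 / 203 | .986 | 2.70 / .88 | 2.762 / .861 | 1.9 |
| Fish oil | 199 / 203 | .996 | 2.75 / .87 | 2.789 / .854 | 1.6 |

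To two decimals the corrected figures are 2.58/.90, 2.60/.90, 2.76/.86 and 2.79/.85. The magnesium difference is 2.6047 before rounding.

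**Check of sizes against Table 1.** Stress active: 66 + 50 + 66 + 60 = 242, as printed. Stress controls: 89 + 63 + 85 + 83 = 320 (Tables 12 and 13: 319). Sodium controls: 82 + 83 + 67 + 63 + 85 + 37 = 417 (Tables 12 and 13: 416). One extra control changes no figure at two decimals.

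**The case against.** The strongest reply is that little depends on these errors, and much of it stands. The stress error is conservative: the protocol claims less power than its inputs deliver. The only adequacy statement for the primary endpoint, at least .90 at 2 mm Hg, survives; its lowest row is fish oil at .901. The supplement errors are under 2 points and at most 0.08 mm Hg, on a secondary endpoint, and no stated threshold separates .85 from .87. Table 1 reports actual numbers randomized for the lifestyle arms and Stage 1, so corrected power cannot alter those sizes. A finished comparison is read from its estimate and interval, not from planned power.

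The reply does not make the printed figures right. The supplement gaps exceed two-decimal rounding, and the stress rows contradict the sizes beside them.

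Two stronger readings are tempting. A reader might infer that both tables are unreliable throughout; the eight reproduced rows rule that out. A reader might also infer that the stress figures were carried over from an earlier, smaller sample. Difference and power agree with each other within each stress row and would fit about 217 to 220 controls against 242 active. But the document shows no such earlier size, so the origin remains a guess.

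**Conclusion.** The point holds for six rows of 14. In the stress management rows the detectable difference is overstated by 9 to 10%, and power is understated by about 4 points (DBP) and 5 points (SBP). In the four supplement SBP rows power is overstated by 1.3 to 1.9 points, so the lower end of the stated SBP range should be .85. The upper end, .98 for sodium, is right.

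This rests on the normal-approximation formula with a square root in the denominator, on the stated SDs, and on the printed sizes. For potassium and fish oil those sizes are the protocol's own Stage 2 estimates, taken at face value. The errors do not show the trial to be underpowered, and they do not overturn the DBP power statement. They are misstated figures that are cheap to correct.

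**What to change.** Recompute the stress rows of Tables 12 and 13 (1.52/.96 and 2.44/.93) and the four supplement rows of Table 13 (calcium 2.58/.90, magnesium 2.60/.90, potassium 2.76/.86, fish oil 2.79/.85). Use the control counts that Table 1 sums to, 417 for sodium and 320 for stress; this changes no result at two decimals. In the section on power for SBP, change the lower bound from .87 to .85, so that the range reads .85 to .98 at 3 mm Hg. Leave the DBP sentence as it is.

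The cost is six table rows, two control counts in each table, and one number in the text. The stress figures improve, the supplement SBP figures become 1 to 2 points less favourable, and no change to design or enrolment is needed.

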The primary outcomes of interest for the lifestyle interventions is the difference between changes in mean DBP from baseline to 18 months between the intervention and comparison groups, with the BP for each participant being determined from nine readings (three readings at each of three visits). The primary endpoint for the supplement interventions is change in DBP from baseline to six months. In the crudest level of analysis, mean change in DBP in each of the actual intervention groups with the control group will be compared in the context of the one-way analysis of variance. At a second level, mean change in DBP between each of the active intervention and control groups will be compared after controlling for clinic. This will be accomplished using multiple regression methods introducing dummy variables for

clinic and intervention group. In addition, more refined analyses will be performed to adjust for other covariates, such as mean initial DBP, age, and sex.

Secondary endpoints in the trial, including changes in SBP and the development of hypertension, will also be examined. The former will be evaluated in the same manner as changes in DBP described above. The development of hypertension will be defined as either going on antihypertensive medications during the course of the trial or attaining a mean DBP greater than or equal to 95 mm Hg based on nine readings over three visits at any point in the trial.

While change in DBP from baseline to termination is the primary outcome of interest, there will also be the opportunity to examine BP measurements taken throughout the follow-up period. In particular, slopes of BP over time will be compared based on available data per participant. Slopes in different treatment groups will also be compared using analysis of variance and regression methods as discussed above. More sophisticated methods of longitudinal data will be utilized to characterize more complex changes in BP over time (105-107). In addition, BP change from baseline to the 12-month follow-up point for lifestyles interventions will also form the basis for planning for Phase II of TOHP.

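### Adjustment of SBP change for baseline SBP is allowed but not made the main analysis, leaving unsecured a free variance gain of about 4–8%, at most 10–10.5%.

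*Protocol*

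**What the plan says.** The Data Analyses section sets out three levels for DBP change: a one-way analysis of variance on raw change, a regression with dummy variables for clinic and intervention group, and then "In addition, more refined analyses will be performed to adjust for other covariates, such as mean initial DBP, age, and sex". For change in SBP, a secondary endpoint, it says "The former will be evaluated in the same manner as changes in DBP described above". No level is designated as the main analysis. Initial DBP is the only baseline blood pressure given as an example.

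The section Power Calculations: SBP uses the variance of raw change, 2V(1−ρ), and concludes "All tests will have between .87 and .98 power to detect a 3 mm Hg change in SBP". The Eligibility Criteria restrict DBP to 80–89 mm Hg on the mean of nine readings and set no range for SBP. Ascertainment of Blood Pressure calls SBP a major secondary endpoint and bases baseline and termination values on nine readings each.

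**The concern.** A change score in effect fixes the coefficient of termination on baseline at 1. When the tracking correlation ρ is below 1 and baseline varies freely, regression on the baseline gives the same expected treatment contrast with a smaller variance. The gain depends on how much baseline variation remains among those enrolled. The entry window removes most of it for DBP but does not act directly on SBP.

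The protocol puts the less efficient contrasts first, bases its SBP power on raw change, and leaves baseline to a level whose covariates are only illustrated. At stake are a modest loss of precision for SBP and, since no level is designated, several possible SBP estimates per intervention.

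**Working it through.** **Inputs from the protocol**
- V for SBP: "the estimated variance of the mean SBP (averaged over three visits with three readings per visit) at baseline or termination is 249.06". Check: 233.13 + 43.39/3 + 13.16/9 = 249.06.
- ρ for SBP: .80 at 6 months, .79 at 18 months. For DBP: V = 118.85, ρ = .84 and .83.
- Test: "Power calculations assume a two-sided test with significance level 0.05". This is stated for DBP and taken here to apply to SBP.
- Group sizes and the 3 mm Hg difference: Table 13. Fish oil is 199 against 203.

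**Step 1. Reproduce the plan's figures.** Variance of change = 2V(1−ρ).
- 6 months: 2 × 249.06 × .20 = 99.62 (SD 9.98).
- 18 months: 2 × 249.06 × .21 = 104.61 (SD 10.23).

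Both match the protocol. Power = Φ(3/SE − 1.96), with SE = SD × √(1/n₁ + 1/n₀). For fish oil, SE = 9.98 × √(1/199 + 1/203) = 0.996 and power = .854 (stated .87). Six of the seven rows of Table 13 reproduce within 2 points. Stress management does not (.931 computed, .88 stated); that is a separate matter.

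**Step 2. Own-baseline adjustment, no narrowing of baseline SBP.** Variance = V(1−ρ²).
- 6 months: 249.06 × (1 − .64) = 89.66, which is 10.0% lower.
- 18 months: 249.06 × (1 − .6241) = 93.62, which is 10.5% lower.

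The proportional gain is (1−ρ)/2. It is a ceiling, since any narrowing of baseline SBP reduces it.

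| Row | Power, raw change | Power, adjusted |
|---|---|---|
| Sodium | .978 | .987 |
| Weight | .921 | .946 |
| Calcium | .904 | .930 |
| Magnesium | .897 | .925 |
| Potassium | .861 | .894 |
| Fish oil | .854 | .888 |

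The increase runs from about 1 to about 3.5 points.

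**Step 3. Allow for the DBP window.** Let k be the fraction of baseline variance left after selection. Then the variance of change is V(1−ρ²) + (1−ρ)²kV, and the gain is (1−ρ)²k / [(1−ρ²) + (1−ρ)²k]. This assumes that selection acts on baseline SBP only through its correlation with baseline DBP, and that the regression of termination on baseline SBP is unchanged.
- DBP itself: if entry values are roughly uniform over a 9.9 mm Hg span, variance = 9.9²/12 = 8.17 and k = 8.17/118.85 = .069. The gain is 0.59% at 6 months and 0.63% at 18 months.
- SBP: k = 1 − r²(1 − .069), where r is the SBP–DBP correlation. The protocol gives no r, so a range is shown.

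| Assumed r | k | Gain, 6 months | Gain, 18 months |
|---|---|---|---|
| 0 | 1.000 | 10.0% | 10.5% |
| .5 | .767 | 7.9% | 8.3% |
| .7 | .544 | 5.7% | 6.0% |
| .8 | .404 | 4.3% | 4.5% |
| .9 | .246 | 2.7% | 2.8% |

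For fish oil with r = .5 to .8, the raw-change variance is 97.30 to 93.69 and its power .862 to .874. Adjustment again takes power to .888, a rise of 2.6 to 1.4 points.

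**Step 4. Chance imbalance.** A 1 mm Hg difference in baseline SBP moves the raw-change contrast by 1 − ρ, about 0.2 mm Hg, against a standard error near 1.0 for fish oil. This is the source of the variance already counted in Step 2 and is not a second loss.

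**The case against.** A reader might infer that the plan gives up the gain, or that SBP will be adjusted only for initial DBP. The text does not support either. The third-level covariates are examples, age and sex are among them, the adjusted analyses are to be carried out, and carrying the DBP method over to SBP most naturally makes initial SBP the matching covariate. The gain is therefore unsecured rather than lost.

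It can also be said that exact covariates for a secondary endpoint belong in an analysis plan, which may exist but is not shown, and that a change-score comparison under randomization is unbiased with a valid type I error rate. Both points are right, and they limit this to a recommendation. They do not remove it, because the protocol itself lays out the order of models and puts baseline in the least specified one.

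The size is modest. The 10% figure is a ceiling, and the lower figures rest on an assumed correlation. Nor can one say that the supplement rows as a group have the lowest SBP power: Table 13 gives stress management .88, below calcium (.92) and magnesium (.91) and level with potassium. Only fish oil, at .87, is lowest.

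**Conclusion.** The point holds as a free improvement to the SBP analysis. Own-baseline adjustment is allowed but not designated as the main model. Making it so would cut SBP variance by up to 10.0% (6 months) or 10.5% (18 months) on the protocol's own V and ρ, or by about 4–8% with an SBP–DBP correlation of .5 to .8, which is an assumption. At the ceiling this is about 1 to 3.5 power points by row, and less if the DBP window narrows baseline SBP. For the primary DBP endpoint the gain is about 0.6%, assuming roughly uniform entry values, so no primary comparison is materially affected. A reader might take this as a bias or validity problem in the change-score comparison; nothing in the protocol supports that.

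**What to change.** State in Data Analyses that the main model for each blood pressure endpoint is a regression on treatment, clinic and that endpoint's own nine-reading baseline (initial SBP for SBP, initial DBP for DBP), with raw change reported descriptively. Further covariates can stay in the more refined analyses. The cost is a sentence of wording: SBP and DBP are already measured at baseline on every participant, and no sample size or procedure changes. The power in Table 13 can stand as a slightly conservative figure on this point, or be recomputed with V(1−ρ²).
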